7.4 Interim Analyses and Data Monitoring

No interim analysis is planned for this study. However, an independent Event Adjudication Committee (EAC) will be set up to evaluate the cardiovascular events.

7.5 Independent Event Adjudication Committee (EAC)

The study will have an independent EAC to adjudicate the cardiovascular events. The cardiovascular events are defined as:

- Death
- Myocardial Infarction
- Hospitalisation for Unstable Angina
- Stroke & TIA (fatal & non-fatal)
- Urgent Revascularisation Procedures
- Hospitalisation for Heart Failure

The adjudicated cardiovascular events will be used for the safety analyses.

7.6 Multi-center Studies and Pooling of Centers

This study will be conducted at approximately 35 sites in China. Data from all sites will be pooled and pooled data will be used for summary tables and analyses.

7.7 Multiple Comparisons/Multiplicity

Not applicable for this study as there is no multiple comparison and no interim analysis is planned.

7.8 Use of an “Efficacy Subset” of Subjects

Subjects in Full Analysis Set (FAS) who complied with the protocol (i.e. no major protocol violations), who have completed at least 8 weeks of double blinded medication and who have >75% treatment compliance with the investigational product (MP-513 or placebo) during the Double-blind treatment period will form a Per-Protocol set (PPS). Major protocol deviations will be assigned during Blind Data Review Meeting (BDRM) that will be held before database lock.

Analysis based on PPS will serve as a supportive analysis for primary efficacy endpoint.

The FAS and PPS are defined in section 8.3.

7.9 Active-Control Studies Intended to Show Equivalence

Not applicable to this study.

7.10 Examination of Subgroups

Exploratory sub-group analysis will be performed for the primary efficacy i.e. change in HbA1c from baseline to Week 24 for following subgroups:

- Gender (male and female)
- Body Mass Index (BMI) (<20 kg/m², 20 ≤ BMI <25 kg/m², 25 ≤ BMI<30 kg/m², BMI≥30 kg/m²)
- Age (<40 years, 40≤ Age<50 years, 50≤ Age <60 years, 60≤ Age <70 years, Age ≥70 years, Age <65 years and Age ≥65 years)
- Alcohol history (Abstainer, >28 units of alcohol per week and ≤28 units of alcohol per week)
- Baseline HbA1c (<7.0%, 7.0% ≤ HbA1c<8.0%, 8.0% ≤ HbA1c<9.0%, HbA1c≥9.0%)
- Baseline FPG (<130 mg/dL, 130 mg/dL≤FPG<160 mg/dL, 160 mg/dL≤FPG<200 mg/dL, FPG≥200 mg/dL)
- Duration of diabetes (<1 year, 1≤ Duration<5 years, 5≤ Duration<10 years, Duration≥10 years)
- Metformin total daily dose (<1000 mg, 1000≤ Metformin<1500 mg, Metformin ≥1500 mg)

8 STATISTICAL ANALYSIS

8.1 Disposition of Subjects

The number and percentage of subjects randomized, completed, and discontinued during the study, as well as the reasons for all post-randomization discontinuations, will be summarized by treatment groups. The number of placebo run-in subjects who do not meet randomization criteria will also be presented in the disposition summary table.

A listing of all subjects who discontinued the study after randomization and placebo-run in subjects who do not meet randomization criteria will be provided. This will also include the specific reason for discontinuation.

8.2 Protocol Deviations

Potential deviations will be identified prior to database lock.

All protocol deviations will be reviewed in a blinded fashion during the blind review of the data and will be described in more detail in the minutes of blind data meeting. The sponsor review team will approve all the final protocol deviation assignments. Once all protocol deviation determinations are finalized and approved, the database will be locked and the treatment codes will be unblinded for statistical analysis.

Number and percentage of subjects with at least one major protocol deviations will be summarized by treatment group and overall.

A listing of all major protocol deviations by subjects to determine reasons for exclusion from the FAS and PPS will be presented.

8.3 Analysis Populations

The study will use following analysis populations for data summarization. Number and percentage of subjects in each analysis set will be summarized by treatment group and overall.

Table 6: Analysis Population

Population	Definition	Displays	Note
All Subject Set	The All Subject Set includes all subjects who were screened	Displays on subject disposition	The subjects will be analyzed for disposition
Randomized Set	The Randomized Set includes all subjects who were randomized	Displays on subject population and major protocol deviations	The subjects will be analyzed according to the treatment to which they were randomized to, irrespective of treatment received
Full Analysis Set (FAS)	The FAS includes all subjects in the randomized set who have received at least one dose of study medication during the double-blind treatment period and have at least one post-baseline efficacy observation. Subjects who were not diagnosed with type 2 diabetes mellitus will be excluded.	Displays related to demography, other baseline characteristics and all efficacy analyses	The subjects will be analyzed according to the treatment to which they were randomized to, irrespective of treatment received
Per-Protocol Set (PPS)	The PPS includes subjects in the FAS who have no major protocol violations, who have completed at least 8 weeks of double-blinded medication and who have > 75% treatment compliance with the investigational product (MP-513 or placebo) during the Double-blind treatment period.	Demographics and Primary efficacy analysis	All protocol violations will be defined in more detail in the blind review document at a Blind Data Review Meeting that will be held before database lock. The subjects will be analyzed according to the treatment to which they were randomized to, irrespective of treatment received.
Safety Analysis Set	The Safety Analysis Set includes all subjects in the randomized set who have received at least one dose of study medication during the double-blind treatment period.	Displays related to demography, other baseline characteristics and all safety analyses	The subjects will be analyzed as MP-513 if the subjects received MP-513 at least once, irrespective of treatment to which they were randomized to. In other cases, the subjects will be analyzed according to the treatment they were randomized to.

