- MP-513 or placebo will be dispensed to the subjects. Unused medication has to be returned to the site.
- Subjects are to be instructed that they have to return for the next scheduled visit day.

Treatment Visit 2 (Week 8 plus/minus 7 days of treatment)

The following observations/procedures are to be performed and checked:

- Vital signs, body weight
- Review use of concomitant treatments and of the regular metformin therapy
- Blood and urine is to be drawn and sent to the central laboratory according to the local procedure for evaluation of haematology, clinical chemistry, urinalysis, HbA1c, FPG, fasting insulin, C-peptide and glucagon
- Evaluation for any AEs including hypoglycaemic episodes experienced by the subjects since last visit
- Review subject diary
- MP-513 or placebo will be dispensed to the subjects. Unused medication has to be returned to the site.

- Subjects are to be instructed that they have to return for the next scheduled visit day.

Treatment Visit 3 (Week 12 plus/minus 7 days of treatment)

The following observations/procedures are to be performed and checked:

- Vital signs, body weight and ECG
- Review use of concomitant treatments and of the regular metformin therapy
- Blood and urine is to be drawn and sent to the central laboratory according to the local procedure for evaluation of haematology, clinical chemistry, urinalysis, HbA1c, FPG, fasting insulin, C-peptide and glucagon
- Review subject diary
- Evaluation for any AEs including hypoglycaemic episodes experienced by the subjects since last visit
- MP-513 or placebo will be dispensed to the subjects. Unused medication has to be returned to the site
- Subjects are to be instructed that they have to return for the next scheduled visit day.

Treatment Visit 4 (Week 16 plus/minus 7 days of treatment)

The following observations/procedures are to be performed and checked:

- Vital signs, body weight
- Review use of concomitant treatments and of the regular metformin therapy
- Blood and urine is to be drawn and sent to the central laboratory according to the local procedure for evaluation of haematology, clinical chemistry, urinalysis, HbA1c, FPG, fasting insulin, C-peptide and glucagon
- Evaluation for any AEs including hypoglycaemic episodes experienced by the subjects since last visit
- Review subject diary
- MP-513 or placebo will be dispensed to the subjects. Unused medication has to be returned to the site

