4.5 Determination of Sample Size

The sample size was estimated based on the primary efficacy variable for assessing treatment difference in mean change in HbA1c from baseline at Week 24 between MP-513 and placebo. The data used for samples size calculation was based on the studies of MP-513 in Japan and other Dipeptidyl Peptidase-4 (DPP-4) inhibitors in China. For a two sided t-test of difference with 0.05 significance level and 90% power of test, 86 subjects per treatment group is required to detect a treatment difference of 0.5% in mean change in HbA1c from baseline at Week 24 with a common standard deviation of 1.0%.

Considering the drop-out rate of 30% and China Food and Drug Administration (CFDA) (on drug registration Code 28) requirement of at least 100 pairs of subjects to be enrolled in a phase 3 study, a total of 240 subjects (120 subjects per treatment group) are required to be randomized in this study.

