6.8.1.1 Definitions

Treatment Emergent Adverse Events (TEAEs):

TEAEs are defined as any AEs or hypoglycaemia episodes that occur or worsen (increase in severity) on the same day or after randomized.

The following rules will apply in cases where the start date of an AE is known:

- If the AE onset date is prior to Day 1, then the AE will not be considered a TEAE.
- If the AE onset date or date of AE worsening is equal to or later than Day 1, then the AE will be considered a TEAE.

The same rule will be applied in cases where start date of a hypoglycemic episode is known.

Refer section 7.3.1 to identify TEAE status when start date of an AE or hypoglycaemia episodes is unknown.

Adverse Drug Reactions (ADRs):

ADRs are defined as TEAE whose causal relationship to study drug is “Reasonable possibility”. If the causal relationship to study drug is missing, then that TEAE will be treated as ADR.

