8.8 Analysis of Safety

All safety data will be summarized by treatment groups using the Safety Analysis Set. No formal statistical test would be performed to determine statistical significance between treatment groups.

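### SAP Table 6 keeps a subject randomised to MP-513 who took only placebo in the MP-513 safety group, so the safety set is not a consistent as-treated set

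*SAP*

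**What the plan says.** SAP 8.3, Table 6 sets the entry condition for the safety set: "The Safety Analysis Set includes all subjects in the randomized set who have received at least one dose of study medication" in the double-blind period. Either product satisfies it. The note in the same row then assigns the arm in two sentences. The first is "The subjects will be analyzed as MP-513 if the subjects received MP-513 at least once, irrespective of treatment to which they were randomized to". The second is "In other cases, the subjects will be analyzed according to the treatment they were randomized to".

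For the Randomized Set, the FAS and the PPS, the same table analyses subjects as randomised, whatever they took. Only the safety row brings in the product received.

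SAP 8.8 applies the set throughout: "All safety data will be summarized by treatment groups using the Safety Analysis Set". It plans no formal test between arms. Treatment-emergent status (SAP 6.8.1.1) depends on dates alone: "If the AE onset date or date of AE worsening is equal to or later than Day 1, then the AE will be considered a" treatment-emergent event. It makes no reference to which product had been taken. The protocol's own definition (6.9.1.3) gives entry conditions for the safety set and no rule for assigning arms.

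**The concern.** An as-treated safety set should place each subject by what was taken. The first sentence of the note does so for anyone given MP-513. The second reverts to the randomised arm for everyone else, and that group includes subjects randomised to MP-513 who never received it. They are reported as exposed to a drug they did not take. A placebo subject can move to MP-513, but no subject can move the other way.

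The safety comparison is half of the study objective and is read from counts and percentages side by side. Exposure is affected as well. SAP 6.6 computes duration from visit dates, and SAP 8.6 summarises it on the safety set, so such a subject adds up to 24 weeks of apparent MP-513 exposure with none taken.

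**Working it through.** **1. Apply the note to every combination of randomised arm and product received.**

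| Randomised to | Received in double-blind period | Sentence that applies | Analysed as |
|---|---|---|---|
| MP-513 | MP-513 at least once | first | MP-513 |
| Placebo | placebo only | second | placebo |
| Placebo | MP-513 at least once | first | MP-513 |
| MP-513 | placebo only | second | MP-513 |

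The last row is the misclassification.

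**2. Look for an override.** There is none in protocol 6.9.1.3 or in SAP 6.6, 6.8.1, 8.6, 8.8 and 8.8.1. Mixed or wrong exposure is possible in principle because product is handed out repeatedly. Protocol 6.6.1 says at the treatment visits: "MP-513 or placebo will be dispensed to the subjects. Unused medication has to be returned to the site".

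**3. Arm size.** The plan gives no figure for wrong-product subjects. The only design figure needed is the 120 per arm of SAP 4.5. Its basis reproduces: a two-sided 5% t-test for a difference of 0.5 with SD 1.0 and 90% power needs 85.03, rounded up to 86 per group as stated (power at 86 is 90.3%). Allowing for 30% drop-out gives 86/0.70 = 122.9, or 123, close to the stated 120. The point does not depend on this, and 120 is used below.

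**4. Effect per misclassified subject.** Let m be the number of MP-513-randomised subjects who took only placebo. The MP-513 rate under the SAP rule is

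[(120 − m) × p_drug + m × p_placebo] / 120,

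which is p_drug − m × (p_drug − p_placebo)/120.

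As an assumption, take the double-blind rates of study 3000-A7 (protocol section 4): adverse events 61.2% and 46.5%, adverse drug reactions 11.7% and 2.0%. That study ran 12 weeks double-blind on a thiazolidinedione background, so the rates are illustrative only. The shift per subject is 14.7/120 = 0.12 percentage point for adverse events and 9.7/120 = 0.08 for adverse drug reactions.

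| m | MP-513 AE rate | AE difference (points) | MP-513 ADR rate | Placebo-only subjects with an AE shown under MP-513 (m × 0.465) |
|---|---|---|---|---|
| 0 (same as as-treated) | 61.2% | 14.7 | 11.7% | 0 |
| 1 | 61.1% | 14.6 | 11.6% | 0.5 |
| 3 | 60.8% | 14.3 | 11.5% | 1.4 |
| 5 | 60.6% | 14.1 | 11.3% | 2.3 |
| 12 | 59.7% | 13.2 | 10.7% | 5.6 |

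If p_drug equals p_placebo, the formula returns the same rate for every m.

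**5. How many such subjects to expect.** A subject reaches the last row of the first table only if every kit taken held placebo. In practice that means a wrong first kit followed by leaving before the second dispensing, or an error repeated at every dispensing. Three assumptions give a rough figure:

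- The 30% drop-out is spread evenly over six 4-week intervals, so 5% leave in the first.
- Errors are independent, at 0.1% to 0.5% per dispensing.
- Every wrong kit holds placebo.

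The first route then gives 120 × 0.05 × 0.001 = 0.006 to 120 × 0.05 × 0.005 = 0.03 subjects. The second route is negligible under independence. A systematic fault, such as a miscoded kit list, would break that assumption.

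**The case against.** The strongest answer is that the case is practically empty. Kits are assigned through the IWRS, and on the assumptions above the expected number is a few hundredths of a subject at most. No formal safety test depends on the rule. SAP 7.1 plans listings of all CRF data, SAP 8.8.1 listings of adverse events, and SAP 8.2 a listing of major deviations. All of that stands, and it is why the point is minor. It does not make the classification right. The deviation listing is also framed around exclusions from the FAS and PPS, so no planned output is specified to show who received the wrong product.

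A second answer is that the note is deliberately cautious, in line with the worst-case handling of missing causality, missing severity and unknown onset dates elsewhere in the SAP. That defends the first sentence: counting any exposure as exposed is a common convention. It does not defend the second, because retaining unexposed subjects in the MP-513 group can hide an excess risk.

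A reader might go further and ask for the events of a placebo subject given MP-513 in error to be split between arms by onset date. The documents do not show that this is needed. It would put one subject in both denominators, and the SAP has no matching rule for laboratory, vital-sign and ECG changes from baseline, or for exposure.

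**Conclusion.** Wrong as written, minor. The second sentence of the note classifies a subject who never took MP-513 as exposed to it, and nothing elsewhere in the documents corrects this. The size is about 0.1 percentage point in the adverse-event rate per such subject of 120, on the assumed 3000-A7 rates. It is zero if no such subject exists, and the expected number is very small unless errors are systematic.

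A reader might infer that the rule inflates MP-513 event rates, since events on placebo are counted under the drug. That holds for raw counts only. The subject enters the denominator too: with equal true rates the expected MP-513 rate is unchanged, and if the drug raises the rate, the result is dilution towards placebo. An apparent excess under MP-513 arises only if the misplaced subject is chosen because he or she had an event.

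**What to change.** In SAP 8.3, Table 6, replace the last sentence of the Safety Analysis Set note with: *Subjects who received only placebo during the double-blind period will be analysed as placebo, irrespective of randomised treatment.* Keep the first sentence. Add a listing of all subjects whose product received differed from the randomised arm, with the dates of the mismatched kits.

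The cost is one sentence and one listing. The data already exist: protocol 6.4.2 provides for a kit code list, and 6.4.6 for dispensing records by subject and date. The wording should be settled before unblinding. It can be applied only afterwards, when kit contents are known. Sample size and efficacy analyses are untouched.

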8.4 Demographic and Other Baseline Characteristics

Demographic and baseline characteristics will be summarized using the FAS, PPS and safety populations. No formal statistical test would be performed to determine statistical significance between treatment groups.

8.4.1 Demographics

Age, height, body weight (at screening), body mass index (BMI) in kg/m^2 and Metformin total daily dose will be summarized as continuous variables by treatment group and overall using descriptive statistics.

Gender and race will be summarized as categorical variables by treatment group and overall using frequency counts and percentages.

Duration of diabetes mentioned in section 6.4 will be summarized descriptively by treatment groups and overall.

Alcohol history will be categorized as:

- Abstainer
- ≤ 28 units of alcohol per week
- > 28 units of alcohol per week

These will be summarized by treatment group and overall using frequency counts and percentages. All demographic characteristics will be presented in full subject listings.

8.4.2 Medical History

A full subject listing of medical history will be presented.

8.5 Prior and Concomitant Therapy

A full subject listing of prior and concomitant medications will be presented.

8.6 Extent of Exposure and Compliance to Study Treatment

Extent of Exposure and Compliance to Study Treatment will be summarized using the FAS, PPS and safety populations.

Duration of study drug exposure during the double blind treatment period and treatment compliance during the double blind treatment period will be calculated as mentioned in section 6.6 and will be summarized descriptively.

The treatment compliance during double blind period will also be summarized for compliance $\leq 75\%$ and $> 75\%$ using frequency counts and percentages.

8.7 Analysis of Efficacy Parameters

All efficacy analysis will be performed on FAS unless otherwise stated.

A full subject listing will be presented for efficacy results (HbA1c, FPG, fasting insulin, C-peptide, glucagon, HOMA-IR, HOMA- β and body weight).

8.7.1 Analysis of Primary Efficacy Variable

8.7.1.1 Primary Analysis of Primary Efficacy Variable

The primary efficacy endpoint is to evaluate the change in HbA1c from baseline to Week 24 in the group receiving MP-513 compared with the group receiving placebo in Chinese subjects with

type 2 diabetes mellitus inadequately controlled with metformin accompanying with diet and exercise. The reduction in HbA1c value indicates improvement.

The primary efficacy will be assessed by testing the null hypothesis that, there is no difference in the change in HbA1c from baseline to Week 24 in the group receiving MP-513 compared to the group receiving Placebo. In statistical notation the hypothesis is defined as follows:

Null Hypothesis $H_0: \mu_{MP-513} = \mu_{Placebo}$

Alternate Hypothesis $H_A: \mu_{MP-513} \neq \mu_{Placebo}$

Where μ_{MP-513} : Mean change in HbA1c from baseline at week 24 for MP-513

$\mu_{Placebo}$: Mean change in HbA1c from baseline at week 24 for placebo

The missing HbA1c values at week 24 will be imputed using LOCF approach prior to analysis. The change in HbA1c from baseline to Week 24 (LOCF) will be analysed using analysis of covariance (ANCOVA) with treatment as a fixed effect and baseline value as a covariate in the model.

For the treatment effects and the difference between the treatment groups, the least square means from ANCOVA will be presented along with the corresponding SE and CI. The treatment difference in mean change from baseline will be computed using the model. The p-values for the test of significance, SE and CI of the mean difference will be presented.

The change in HbA1c from baseline for all the post baseline assessments visits, Week 12 (LOCF) and Week 24 (LOCF) will also be summarized as continuous variable using descriptive statistics.

The line graph for mean change in HbA1c from baseline to Week 24 and Week 24 (LOCF) will be presented. The 95% CIs will also be shown in the graph with error bar. The plots of Week 24 and Week 24 (LOCF) will not be connected.

8.7.1.2 *Supportive Analysis of Primary Efficacy Variable*

The study will have two supportive analyses to be performed on primary efficacy variable i.e. change in HbA1c from baseline to Week 24, as follows:

- The change in HbA1c from baseline to Week 24 in MP-513 compared to Placebo will be performed on PPS using the same statistical methodology as described for the primary analysis.
- The change in HbA1c from baseline to Week 24 in MP-513 compared to Placebo will be analysed using mixed effects model for repeated measure (MMRM), with treatment, visit and interaction of treatment and visit as fixed effects and baseline value as a covariate in the model. An unstructured covariance matrix will be used to model the covariance of within-subject values. The Kenward-Roger approximation will be used to estimate denominator degrees of freedom (Kenward and Roger, 1997). For this analysis, missing data will not be imputed, i.e. only the observed data will be used.

